7.1 Primary objective

The primary objective is to monitor and assess the safety of Tresiba[®], used with any other anti-diabetic treatment and according to label, by analysing whether treatment with Tresiba[®] OD is associated with a change in the rate of any hypoglycaemic episodes occurring during the

observation period, compared to the rate of any hypoglycaemic episodes occurring during the baseline period, where the patient continues the prior basal insulin as part of their anti-diabetic treatment regimen. The prior basal insulin can be any type of basal insulin.

7.2 Secondary objective(s)

The secondary objectives are to monitor and assess the safety and effectiveness of Tresiba[®], used with any other anti-diabetic treatment, by analysing whether the treatment with Tresiba[®] OD is associated with a change in safety, effectiveness, PROs, and HE endpoints compared to the baseline period, where the patient continues the prior basal insulin as part of their anti-diabetic treatment regimen. The prior basal insulin can be any type of basal insulin.

7.3 Observational endpoints

All observational endpoints will be collected during the baseline period (4 weeks before Tresiba[®] treatment, at visits 1 and 2) and at the following time points after treatment initiation: 3 months (± 45 days), 6 months (± 45 days), 9 months (± 45 days), and 12 months (± 45 days), when available.

7.3.1 Primary observational endpoint

The primary observational endpoint is the change from the baseline period (4-week baseline period) in the number of any hypoglycaemic episodes occurring during the 12-month observation period with Tresiba[®] (analysed as the change in rate per PYE). Results will also be used in external registration of the study at clinicaltrials.gov and the ENCePP register.

Hypoglycaemic episodes will be collected throughout the study using a 4-week patient hypoglycaemia diary (collected at visits 2, 3, 4, 5, and 6) and 6-month recall for severe hypoglycaemia (visit 1).

7.3.2 Secondary observational endpoints

7.3.2.1 Secondary effectiveness endpoints

- Change from baseline (visit 2) in FPG after 12 months of treatment
- Responder for HbA1c at end of study:
 - HbA1c $< 7\%$ at end of study
 - HbA1c $< 7.5\%$ at end of study
 - HbA1c $< 7\%$ at end of study without severe hypoglycaemic episodes during the last 12 weeks of treatment including only patients exposed for at least 12 weeks
 - HbA1c $< 7.5\%$ at end of study without severe hypoglycaemic episodes during the last 12 weeks of treatment including only patients exposed for at least 12 weeks
 - HbA1c lowered according to national guidelines
- Change from baseline (visit 2) in HbA1c after 3 months of treatment

- Change from baseline (visit 2) in HbA1c after 6 months of treatment
- Change from baseline (visit 2) in HbA1c after 9 months of treatment
- Change from baseline (visit 2) in HbA1c after 12 months of treatment
- Hypoglycaemia
 - Change from the baseline period in the number of hypoglycaemic episodes according to the Novo Nordisk definition as well as to the ADA definition of hypoglycaemia (3), after 12 months of treatment
 - Change from the baseline period in the number of any hypoglycaemic episodes during “the maintenance period” (ie, after 16 weeks of treatment)
 - Change from the baseline period in the number of any nocturnal (00:01-05:59 am) hypoglycaemic episodes during “the maintenance period” (ie, after 16 weeks of treatment)
 - Change from the baseline period in the number of any nocturnal (00:01-05:59 am) hypoglycaemic episodes after 12 months of treatment
 - Change from the baseline period in the number of any hypoglycaemic episodes occurring during sleep in the time span 22.01pm and 07.59am, that results in the patient being awoken after 12 months of treatment
 - Change from the baseline period in the number of non-severe hypoglycaemic episodes after 12 months of treatment
 - Change from the baseline period in the number of any hypoglycaemic episodes in high dose users (defined as patients using >80 U daily) after 12 months of treatment
 - Change from the baseline period in the number of any hypoglycaemic episodes in hypoglycaemia prone (hypo-prone) patients after 12 months of treatment; hypo-prone patients are defined as having any of the below:
 - a) experienced at least 1 severe hypoglycaemic episode within the last year (according to the ADA definition, April 2013 (3))
 - b) moderate chronic renal failure, defined as glomerular filtration rate 30-59 mL/min/1.73 m² per the CKD-Epi, as specified by physician statement (or according to national reference definitions if they differ from the values stated)
 - c) hypoglycaemic symptom unawareness (history of impaired autonomic responses [tremulousness, sweating, palpitations, and hunger] during hypoglycaemia)
 - d) for T1DM: DM duration for more than 15 years
 - e) for T2DM: exposed to insulin for more than 5 years

7.3.2.2 Secondary safety endpoints

- Change from the baseline period in the number of severe hypoglycaemic episodes after 12 months of treatment
- Change from baseline (visit 2) in daily insulin dose (total, Tresiba[®], bolus) after the observation period

- Change from baseline (visit 2) in the number of SMBG test strips used during the 12 months of treatment
- Change from baseline (visit 2) in body weight after 12 months of treatment
- Frequency of SADRs, MESI (medication errors), and pregnancies during 12 months of treatment

All data reported as counts will be converted to rates per PYE for analysis purposes.

7.3.2.3 Secondary patient reported outcome (PRO) endpoints

HR-QoL questionnaire (SF-36 v2) and DTSQ, and change from baseline on each measure, as appropriate, after 12 months of treatment. The PRO endpoints are described in Section 8.3.2.7.

7.3.2.4 Health economic and dose-time flexibility endpoints

- Physicians primary reason for switching to treatment with Tresiba[®] (see Section [8.3.3.2](#))
- Physicians primary reason for not switching to treatment with Tresiba[®] (see Section [8.3.3.2](#))
- Physicians primary reason for switching to treatment with Tresiba[®] during the baseline period ie, early switchers (see Section [8.3.3.2](#))
- Change from baseline in the following HE-endpoints:
 - Number of outpatient visits due to hypoglycaemia
 - Number of physician or diabetic nursing visits due to hypoglycaemia
 - Number of treatments by a paramedic at home
 - Number of emergency room visits due to hypoglycaemia
 - Number of ambulance transportations due to hypoglycaemia
 - Number of hospitalisations due to hypoglycaemia, and duration of hospitalisation
 - Duration of absence from work due to hypoglycaemia
 - Used SMBG test strips and how many
- Patient preference compared to previous treatment
- FlexTouch[®] pen; preference of this device compared to previous injection method before Tresiba[®] use at the end of the study
- Change from baseline in dose-time flexibility endpoints:
 - Number of missed doses
 - Reason for missed dose
 - Action taken when dose missed
 - Changes in any social, leisure, and working activities due to insulin treatment
 - Number of times Tresiba[®] flexibility option used

All data reported as counts will be converted to rates per PYE for analysis purposes.

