8.1.3 Treatment of patients

Patients with T1DM as well as patients with T2DM requiring insulin therapy will be treated according to routine clinical practice at the discretion of the treating physician. The assignment of the patient to Tresiba[®] is not decided in advance by the protocol but falls within routine practice.

The initiation of Tresiba[®] is at the discretion of the treating physician. All anti-diabetic treatment will be prescribed and used in accordance with local label, including the study product Tresiba[®], marketed as Tresiba[®] (100 units/mL / 200 units/mL) in a prefilled pen injector (FlexTouch[®]).

Tresiba[®] will be prescribed by the physician under routine clinical practice conditions (see Section 8.1.5). The physician will determine the starting dose, based on local label, as well as later changes to dose, if any. Patients will be instructed as per usual practice to use Tresiba[®] as specified in local package insert (ie, OD subcutaneous [SC] administration at any time of the day, preferably at the same time every day). Any other anti-diabetic treatments can be changed or doses adjusted at the discretion of the treating physician.

Diet and exercise counselling may be conducted as per the standard of care at the investigational site.

All other prescription and non-prescription drugs may be used.

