8.2.2 Inclusion criteria

Patients must meet the following inclusion criteria to be eligible for the study.

1. Informed consent obtained before any study-related activities (Study-related activities are any procedure related to recording of data according to the protocol)
2. Male or female patients ≥ 18 years of age at time of informed consent
3. T1DM (diagnosed clinically) prior to inclusion in the study, and/or T2DM, insulin using patients (diagnosed clinically) prior to inclusion in the study
4. Planned initiation with Tresiba[®]

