8.2.6 Flowchart

All visits and data collections are outlined below in [Table 8–1](#).

Table 8–1 Flow chart of study-related data collection

Study NN1250-4189	Planning to initiate	Initiation	Observation period			
			V3 ¹	V4 ¹	V5 ¹	V6 ¹
Visit Number (V)	V1 ¹	V2 ¹	V3 ¹	V4 ¹	V5 ¹	V6 ¹
Time of visit (Months)	-1	0	3	6	9	12
Visit window (days)		+14	±45	±45	±45	±45
PATIENT RELATED INFO/ASSESSMENTS						
Informed consent	X					
In/Exclusion criteria	X	X				
Initiation		X				
Withdrawal criteria		X	X	X	X	X
Demographic data	X					
Height, systolic and diastolic blood pressure (if available)	X					
Body weight (if available)	X	X	X	X	X	X
Diagnosis of diabetes	X					
Insulin use – is the patient a high dose insulin user (>80 U/day)	X					
Hypoglycaemia risk: is the patient prone to hypoglycaemia	X					
Concomitant ill/ medical history	X					
Anti-diabetic treatment type and dose ²	X	X	X	X	X	X
Concomitant medications	X	X	X	X	X	X
Reason for switching or not switching to Tresiba [®]		X				
First date on study insulin (Tresiba [®])		X				

Study NN1250-4189	Planning to initiate	Initiation	Observation period			
SAFETY AND EFFECTIVENESS						
Distribution and collection of patient diaries ³	X	X	X	X	X	X
Most recent FPG and date of measurement (if available)	X	X	X	X	X	X
Most recent HbA _{1c} and date of measurement (if available)	X	X	X	X	X	X
Total daily dose of bolus insulin on day prior to visit (if applicable)		X	X	X	X	X
Changes in any social, leisure and working activities due to insulin treatment		X	X	X	X	X
SADRs, MESI and pregnancies ⁴		X	X	X	X	X
Hypoglycaemic episodes ⁵	X	X	X	X	X	X
PRO questionnaires ⁶ : SF-36 (version 2) DTSQ ⁷	X	X	X	X	X	X
Patient preference			X	X	X	X
End of study						X ⁸

Abbreviations: DTSQ=diabetes treatment satisfaction questionnaire; FPG=fasting plasma glucose; HbA_{1c}=glycated haemoglobin A1c; MESI=medical events of special interest; SADR=serious adverse drug reaction; PRO=patient reported outcomes; SF-36=Short form-36; V=visit.

¹ Decision to initiate the study will take place 4 weeks prior to actual initiation of Tresiba[®] treatment, and with this a statement reported by the physician that use of current medication (for 4 weeks) will not be a safety problem for the patient. Patient material will be handed out at visit 1 to explain the importance of the baseline reporting period. It is not guaranteed that all patients will attend all visits.

² For anti-diabetic treatment also collect the insulin dosing regimen.

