8.3.3.3 Flexibility of dose time and FlexTouch[®] pen device

The effects of dose-time flexibility on compliance and effectiveness will be measured by collecting data from patient diaries. At each visit, the treating physician, or an appropriately trained member of staff, should document the dose-time flexibility responses in the eCRF which will contain specific fields based on the diary.

Patients will be provided with a study diary and requested to prospectively document information on missed doses and dose-time flexibility 4 weeks prior to each physician visit.

Patients will be asked to record/indicate information such as:

- If they miss a dose
- Why they missed a dose
- What did they do when they missed a dose
- How often they needed to take their Tresiba[®] at a different time/used the possibility of dose-time flexibility

In addition, at visits 2-6, the patient will be asked if their insulin treatment required them to change any social, leisure, and working time activities.

At the end of the study, patients will be asked which they found easier to use a) the FlexTouch[®] pen or b) previous injection method.

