8.4.3 Visit 1 Physician plans to initiate Tresiba[®] (Week -4)

The patient will receive complete information about the study both orally and in writing. Informed consent must be given prior to any trial-related data being collected.

The visit will include:

- Signature of informed consent and recording of the date informed consent was given
- Determination of eligibility by checking the inclusion/exclusion criteria (Section [8.2.2](#) and Section [8.2.3](#)). The decision as to which T1DM and T2DM patients will start Tresiba[®] treatment is determined by the treating physician
- Distribution of all PROs to be completed by the patient. This will be done prior to any following steps. The questionnaires will be administered while the subject is in the waiting room or another dedicated room
- Demography – collecting age, sex, ethnicity
- Blood pressure (systolic and diastolic) and height measurements, if available
- Body weight (kg), if available
- Medical history
- Physician will document if the patient is hypo-prone
- Concomitant medications (related to diabetes - including insulin dosing regimen)
- Physician will document if the patient is a high dose insulin user (>80 U/day)
- Collection of the most recent HbA1c and FPG and date of the measurements
- Patients will be interviewed and asked to recall any severe hypoglycaemic episodes in the 6 months prior to this visit
- Distribution of diary and guidance on use.

The patient will be instructed to:

- Continue on current therapy, as prescribed by the physician and lifestyle interventions
- Record in the diary every episode of hypoglycaemia occurring over the following 4 weeks
- Record in the diary insulin dose, time, and date (over the following 4 weeks)
- Record in the diary if any doses are missed and what the patient did
- Record in the diary how many SMBG strips they use over the following 4 weeks
- Record in the diary any resource use due to hypoglycaemia over the following 4 weeks
- Bring the diary to the next clinical visit.

An appointment will be made for their next usual clinical visit (visit 2, initiation) in approximately 4 weeks (+14 days).

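### Missed doses are analysed per patient-year, so a change in the number of scheduled injections at the switch can look like a change in compliance

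*Protocol*

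**What the plan says.** Protocol section 7.3.2.4 includes "Number of missed doses" among the dose-time flexibility endpoints, as a change from baseline. The section closes with the general rule "All data reported as counts will be converted to rates per PYE for analysis purposes". Section 3.6.2 places change in the dose-time flexibility endpoints among the main secondary endpoints. Section 8.7.2.2 analyses interval and ratio-level secondary endpoints in the same way as the primary, with two-sided tests at 0.05.

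Section 8.3.3.3 gives the purpose: "The effects of dose-time flexibility on compliance and effectiveness will be measured by collecting data from patient diaries".

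Missed doses are recorded both before and after the switch. At visit 1 (section 8.4.3) the patient is told: "Record in the diary if any doses are missed and what the patient did". The same instruction recurs for the 4 weeks before each later visit (sections 8.4.4 and 8.4.5).

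On the regimen before the switch, section 7.1 says: "The prior basal insulin can be any type of basal insulin". The eligibility criteria (sections 8.2.2 and 8.2.3) place no limit on how often it was injected; for type 2 diabetes the entry condition is only "T2DM, insulin using patients (diagnosed clinically) prior to inclusion in the study". After the switch, section 8.1.3 describes Tresiba use as "OD subcutaneous [SC] administration at any time of the day, preferably at the same time every day". Section 8.1.1 expects changes in dose interval and in bolus insulin during the study and keeps those patients in the secondary analyses.

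**The concern.** A count of missed doses depends on two things: how many doses were due, and what share of them was missed. Compliance concerns the second. A rate per patient-year divides by time, so it mixes the two. That does no harm if the number of doses due stays constant, but here it can change within the patient at exactly the moment being evaluated.

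A patient who moves from two basal injections a day to one has half as many basal doses to miss. The planned analysis would record fewer missed doses per year with no change in behaviour, and a reader guided by section 8.3.3.3 could take that as better compliance. The protocol also does not say whether a missed dose means basal only or includes bolus. If bolus counts, adding or stopping bolus insulin changes the number of doses due as well.

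**Working it through.** The protocol gives no figure for missed doses, so there is none to reproduce. The 517 completers per diabetes type in section 8.5 concern the primary endpoint and are used below only as a group size.

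**Inputs**
- Scale: rate per patient-year (section 7.3.2.4).
- Basal injections a day after the switch: 1 (sections 7.1 and 8.1.3).
- Share f of patients on two basal injections a day before the switch: not given; assumed range 0 to 50%.
- Probability p of missing a scheduled dose: not given; assumed equal before and after, which is what unchanged adherence means here.

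**Step 1. One patient.** With k scheduled doses a day, missed doses per year = 365.25 × p × k. At an assumed p = 5% and k = 2 before: 365.25 × 0.05 × 2 = 36.5. At k = 1 after: 365.25 × 0.05 × 1 = 18.3. The count halves with adherence unchanged.

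**Step 2. The group, basal doses only.** Mean scheduled doses a day before the switch are (1 − f) × 1 + f × 2 = 1 + f, and after it 1. The ratio after/before is 1/(1 + f) and the apparent fall is f/(1 + f). The probability p cancels.

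| f | f/(1 + f) | Missed doses per year at p = 5% (before → after) |
|---|---|---|
| 0 | 0% | 18.3 → 18.3 |
| 10% | 0.10/1.10 = 9% | 20.1 → 18.3 |
| 20% | 0.20/1.20 = 17% | 21.9 → 18.3 |
| 30% | 0.30/1.30 = 23% | 23.7 → 18.3 |
| 50% | 0.50/1.50 = 33% | 27.4 → 18.3 |

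**Step 3. Bolus doses counted as well.** Assume three bolus doses a day, unchanged and equally often missed. The ratio is 4/(4 + f): 0.98 at f = 10% and 0.89 at f = 50%, so falls of about 2% and 11%.

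**Step 4. Bolus changed after the switch.** At p = 5%, a patient on one basal injection who gains three bolus injections goes from 18.3 to 4 × 18.3, about 73 missed doses a year. Stopping three bolus injections does the reverse. The count can therefore move in either direction.

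**Step 5. Chance of a significant result with adherence unchanged.** A simulation of basal-only counting used 517 patients, a 28-day baseline diary, four 28-day diaries after the switch, p varying between patients (beta distribution, mean 2% or 5%), a paired t-test and 2,000 runs. A significant fall appeared in 28% (mean p 2%) and 61% (mean p 5%) of runs at f = 10%, and in 78% and 99% at f = 20%. At f = 0 it was 2.0% and 2.4%. The protocol plans a regression estimator rather than a t-test, so these figures are indicative.

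**Step 6. With scheduled basal doses as denominator.** Missed over scheduled is p before and p after, a ratio of 1.00 for every f and p.

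**The case against.** The strongest reply is that missed doses per year is a legitimate quantity. It says how often a patient goes without an injection that was due, and having fewer injections due is a real consequence of once-daily dosing. Section 8.3.3.3 also refers to several diary items together (doses missed, why, what was done, changes of timing) and does not name the count alone as the compliance measure. This stands as far as it goes: the count is worth reporting. But it is the one item with a numerical change from baseline that bears directly on compliance, and on a per-year scale it cannot separate adherence from regimen.

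A second reply is that the detail belongs in the SAP. The protocol itself fixes the per-year scale, so a SAP that follows it inherits the problem. Adjusting for baseline covariates does not by itself remove it, because the number of doses due changes within the patient.

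A third reply is that the size is unknown. That is correct: f is not in the documents, section 7.1 leaves injection frequency open rather than stating it, and an equal miss probability on both regimens is an assumption.

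A reader might also infer that the bias always favours Tresiba. The documents do not support that. It holds for basal doses when the prior regimen was at least once daily. If bolus doses count, the bolus changes expected in section 8.1.1 can reverse the sign. Nor does the protocol endorse a causal reading of any fall: section 8.9 says the design allows no causal conclusion.

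**Conclusion.** The point holds for one secondary endpoint. The stated scale lets a change in scheduled injections appear as a change in compliance. For basal-only counting, with equal miss probability per dose and a share f previously on two basal injections a day, the apparent fall is f/(1 + f), which is 9% to 33% for f from 10% to 50% and zero at f = 0. With three bolus doses a day also counted and unchanged, it is about 2% to 11% over the same range. Once bolus use itself changes, neither size nor direction can be stated from the documents.

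It would be too much to infer that the study's main conclusions are at risk. The endpoint is not among those named for external registration in section 7.3.2.5, and the primary endpoint and sample size do not depend on it. The change is worth making because it is small and the protocol has no other safeguard.

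**What to change.** In sections 7.3.2.4 and 8.3.3.3, state that the compliance comparison uses missed basal doses divided by scheduled basal doses in each 4-week diary window: the prior basal insulin in the baseline diary, Tresiba in the later ones. Derive scheduled doses from the regimen already recorded at every visit (Table 8–1 in section 8.2.6: "For anti-diabetic treatment also collect the insulin dosing regimen") together with the diary records of insulin dose and time (section 8.4.1).

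Where the diary entries do not separate basal from bolus, either use all scheduled insulin doses as the denominator, or add a sensitivity analysis restricted to patients on one basal injection a day at baseline. That restriction removes the basal part of the artefact only. Keep missed doses per patient-year as a descriptive summary.

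The cost is endpoint wording and one derived variable. No diary rewording is required; the diary form is not shown, and changing it after data collection has started would mix two wordings. The downsides are that the denominator is approximate when the dose interval changes between visits, and that an apparent improvement may shrink.

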7.3.2.5 Secondary endpoints for external study registration

The following secondary endpoints will be used in external registration of the study at clincialtrials.gov and the ENCePP register:

- Change from baseline in HbA1c and FPG after 12 months
- Change from the baseline period in the number of severe hypoglycaemic episodes after 12 months
- Change from baseline in HR-QoL questionnaire scores (PROs: SF-36 and DTSQ) after 12 months of treatment

8 Research methods

In this document physician refers to the individual overall responsible for the conduct of the non-interventional study at a study site.

